10.0 Criteria for Repeat Assessments, Rescreening, and Discontinuation

Repeat Assessments

Screening assessments can be repeated within the screening window under the same screening number with the exception of eligibility criteria related rating scales/questionnaires. Subject diagnosis confirmation will not be repeated.

Rescreening

Subjects who screen fail may be rescreened one time, under a new screening number. If a subject is rescreened, all screening assessments (with the exception of the diagnosis confirmation) must be repeated and the stability criteria timelines must be met.

Discontinuation

Subjects will be discontinued under the following circumstances:

1. Study Medication Non-Compliance: Significant noncompliance is defined as missing seven or more consecutive days of study medication or more than 24 cumulative days of study medication during the entire study.
2. Subjects who have the following lab values while on study medication:
 - Liver transaminase levels >3 times the ULN
 - Hemoglobin <9
 - White blood cells <1500
 - Serum creatinine >1.5
3. Subjects who develop moderate or severe renal impairment as defined by CrCl <50 ml/min (measured by the Cockcroft-Gault equation) while on study medication
4. Female subjects who become pregnant while on study medication
5. Subjects who require more than 50% increase in their dose of antipsychotic medication OR the addition of a new antipsychotic medication will be reviewed by the principal investigator and discontinuation will be addressed on a case-by-case basis as clinically indicated.
6. Subjects who require treatment with any excluded concomitant medications (See Attachment 2)

If a subject discontinues from the study, discontinuation assessments will be at the discretion of the investigator.

A subject may withdraw from the study medication at any time at his/her own request, or may be withdrawn at any time at the discretion of the investigator for safety, behavioral, or administrative reasons.

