8. Subjects who have participated in a clinical trial with any pharmacological treatment intervention for which they received study-related medication in the 4 weeks prior to screening AND subjects currently receiving treatment (within 1 dosing interval plus 4 weeks) with an investigational depot formulation of an antipsychotic medication.
9. Females who are pregnant or planning to become pregnant or breastfeeding or planning to do so during the study period.
10. Subjects with current acute, serious, or unstable medical conditions, including, but not limited to: inadequately controlled diabetes, asthma, COPD, recent cerebrovascular accidents, acute systemic infection or immunologic disease, unstable cardiovascular disorders, malnutrition, or hepatic or renal disease, renal including renal failure, gastroenterologic, respiratory, endocrinologic, neurologic, hematologic including thrombotic thrombocytopenia purpura/hemolytic uremic syndrome, or infectious diseases
11. Subjects who require concomitant treatment with any other medication other than those allowed as specified in Attachment 2, or with any other medication specifically excluded in Attachment 2.
12. Clinically significant electrocardiogram (ECG) abnormality prior to randomization as defined by: subjects with a corrected QT interval (Bazett's; QTcB) >450 msec (male) or >470 msec (female) prior to randomization. Repeat ECGs will be conducted at the discretion of the principal investigator or medical designee.
13. Test positive for (1) Hepatitis C virus antibody, (2) Hepatitis B surface antigen (HBsAg) with or without positive Hepatitis B core total antibody.
14. Subjects with moderate to severe renal impairment as defined by creatinine clearance (CrCl) < 60 ml/min (measured by the Cockcroft-Gault equation) at screening.
15. Subjects with hepatic impairment as defined by liver transaminases or total bilirubin > 3 × upper limit of normal (ULN).
16. Subjects considered a high risk for suicidal acts – active suicidal ideation as determined by clinical interview OR any suicide attempt in 90 days prior to screening.
17. Subjects who demonstrate overtly aggressive behavior or who are deemed to pose a homicidal risk in the investigator's opinion.
18. Subjects currently receiving cognitive remediation therapy at time of study entry

19. Subjects who have had electroconvulsive therapy (ECT) within 12 months of study entry or who will have ECT at any time during the study.

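### Minor inconsistency: the creatinine-clearance entry limit can admit a subject whose serum creatinine already exceeds the mandatory stopping limit of 1.5

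*Combined protocol and SAP*

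**What the plan says.** **Stopping.** Section 10.0 (Discontinuation, item 2) requires discontinuation of "Subjects who have the following lab values while on study medication". The list includes "Serum creatinine >1.5", haemoglobin below 9, "White blood cells <1500" and transaminases above three times the upper limit of normal. Only the transaminase limit has a stated reference; the other three carry no unit. Item 3 adds a second renal stop, "CrCl <50 ml/min (measured by the Cockcroft-Gault equation) while on study medication". These stops are mandatory. Item 5, on antipsychotic dose increases, is by contrast left to individual review.

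**Entry.** The only numeric renal limit in section 5.0 is exclusion 14: "Subjects with moderate to severe renal impairment as defined by creatinine clearance (CrCl) < 60 ml/min", by Cockcroft-Gault at screening. There is no serum creatinine limit and no numeric haemoglobin or white-cell limit. Exclusion 10 covers "Subjects with current acute, serious, or unstable medical conditions", and its list includes renal and haematologic disease, but it gives no laboratory value. Exclusion 15 ("Subjects with hepatic impairment as defined by liver transaminases or total bilirubin" above three times the upper limit) uses the same transaminase figure as the stop.

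**Timing.** Attachment 1 schedules the metabolic panel, blood count and creatinine clearance at visits 1, 6 (day 56) and 10 (day 112). MATRICS is scheduled at visits 2, 6 and 10. Section 11.0 requires abnormal results to be repeated only when they arise after randomisation.

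**The concern.** Clearance depends on age, sex and weight as well as creatinine, so a clearance floor caps creatinine at a different level for each subject. Where that cap lies above 1.5, a subject can pass screening with a creatinine that section 10.0 treats as a reason to stop. The screening value itself triggers nothing. If the value is the same at visit 6, however, the protocol's own rule removes the subject for something known at visit 1.

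What is at stake is an avoidable early stop. The visit 10 primary-outcome score may be lost, because section 10.0 leaves assessments at discontinuation to the investigator. The stop would also count in the retention-time comparison of section 16.0, although it would say nothing about tolerability.

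**Working it through.** The plan gives no figure on this point, so there is none to reproduce. The check uses the equation that the protocol names.

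**Inputs**
- Ages 18 to 40; entry clearance of at least 60 ml/min (section 5.0).
- Stops at creatinine above 1.5 and clearance below 50 ml/min (section 10.0).
- Assumed: creatinine in mg/dL, actual body weight in the equation, and weights of 50 to 100 kg. The documents give no weight distribution and do not say which weight is to be used.

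**Formula.** Clearance = (140 − age) × weight / (72 × creatinine), multiplied by 0.85 for women.

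**Step 1: one subject.** For a man aged 25 weighing 80 kg, (140 − 25) × 80 = 9200.
- Creatinine 1.6: 9200 / 115.2 = 79.9, so he is eligible.
- Creatinine 1.5: 9200 / 108 = 85.2. For him the creatinine stop is 85.2 − 60 = 25.2 ml/min stricter than entry.
- Creatinine at the entry limit: 9200 / (72 × 60) = 2.13.
- Creatinine at the clearance stop: 9200 / (72 × 50) = 2.56. That stop is looser than entry, so the two renal stops lie on opposite sides of the entry limit.
- He avoids the stop only if creatinine falls by at least 1 − 1.5/1.6 = 6.3%, or by 29.6% if he enters at 2.13.

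**Step 2: who can be affected.** Setting creatinine to 1.5 and clearance to 60 gives the weight above which overlap is possible: 60 × 72 × 1.5 / (140 − age) = 6480 / (140 − age), divided by 0.85 for women.

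| Age | Men | Women |
|---|---|---|
| 18 | 53.1 kg | 62.5 kg |
| 25 | 56.3 kg | 66.3 kg |
| 40 | 64.8 kg | 76.2 kg |

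**Step 3: range over weight.** The highest creatinine allowed at entry, at age 30:

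| Weight | Men | Women |
|---|---|---|
| 50 kg | 1.27 | 1.08 |
| 60 kg | 1.53 | 1.30 |
| 80 kg | 2.04 | 1.73 |
| 100 kg | 2.55 | 2.16 |

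Lighter subjects are not affected. At 60 kg the cap is 1.39 for a man aged 40 and 1.36 for a woman aged 25.

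**Step 4: cost of one lost visit 10 score.** Of 70 seropositive subjects, one is 1.4%.
- Visit 10 comparison alone: standard error × √(70/69) = 1.007, a rise of 0.7%.
- Planned mixed model, treatment effect averaged over visits 6 and 10: with equal variances, residual correlation r and missing fraction m = 1/70, the variance ratio is 1 + [(1 − r)/2] × m/(1 − m), where m/(1 − m) = 1/69. The standard error is multiplied by 1.0025 at r = 0.3, 1.0018 at r = 0.5 and 1.0011 at r = 0.7 (r is assumed).

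No calculation applies to haemoglobin or white cells; that part rests only on the absence of a number at entry.

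**The case against.** The strongest reply is that nothing of consequence has been shown. The number of affected subjects may be zero. Visit 6 bloods and visit 6 MATRICS fall at the same visit, so a subject stopped on those bloods would normally already have contributed one of the two post-baseline scores. An assessment at discontinuation is discretionary, not ruled out. All of this stands, and it limits the point to a minor one.

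A second reply is that existing provisions cover the gap. Section 10.0 says "Screening assessments can be repeated within the screening window under the same screening number", the investigator sees the visit 1 results, and exclusion 10 allows exclusion on judgement. This stands in part. For haemoglobin and white cells it is persuasive, since values that low may well be caught. For creatinine it is weaker: a stable 1.6 with a clearance of 79.9 need not count as serious or unstable disease, and with no limit at entry nothing prompts a repeat.

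A third reply concerns the remedy. Excluding the example man turns a possible later stop into certain non-entry, and an entry limit equal to the stop leaves no margin, unlike the 60 and 50 clearance pair. Both remarks are fair, and they are why amending the stop is offered as an alternative.

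Finally, the overlap depends on the weight used. If sites used ideal or lean weight and that was lower than actual weight, the overlap would shrink, most noticeably in women.

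**Conclusion.** The inconsistency is real but minor, and mainly concerns creatinine. Exclusion 14 admits subjects already beyond the creatinine stop, over weights that are ordinary for men aged 18 to 40 and moderately high for women. Such a subject must be stopped at visit 6 if creatinine has not fallen to 1.5 or below. Only the visit 10 score is then at risk, and each such loss among seropositive subjects raises the standard error of the planned averaged effect by about 0.1% to 0.25%. The conclusion assumes mg/dL and actual body weight. The documents give no distribution of creatinine or weight, so the number affected is unknown, probably small and possibly zero.

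A reader might infer three stronger things that the documents do not support:
- **That unsafe subjects are enrolled.** A clearance of 79.9 is well inside the protocol's own entry limit, so no toxicity risk has been shown.
- **That the comparison is biased or underpowered.** The mismatch concerns values fixed before randomisation and applies equally to both arms. Planned sample size and alpha are untouched.
- **That haemoglobin and white cells have no safeguard at entry.** Exclusion 10 covers haematologic disease in words; only a number is missing.

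**What to change.** Add one exclusion to section 5.0: a visit 1 serum creatinine above 1.5 mg/dL, repeatable within the screening window. Confirm the unit and print it in sections 5.0 and 10.0.

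If the sponsor regards these subjects as safe to enrol, change the stop instead. One option is to drop the absolute creatinine limit and rely on the existing clearance stop of 50 ml/min; for the example man that would allow creatinine up to 2.56, which is a clinical decision. The other is to define the stop as a rise from baseline.

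As a lesser point, the same exclusion can mirror the haemoglobin and white-cell stops (below 9 g/dL and below 1500 per microlitre, units to be confirmed).

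The cost is protocol wording. The blood is already drawn at visit 1, so no visit or sample is added. Expect a few more screen failures, softened by the repeat provision and the single rescreen that section 10.0 allows. With the entry limit set equal to the stop, a subject just under 1.5 can still cross it through ordinary variation, so early stops would be reduced but not eliminated. The change does not address the discretionary assessments at discontinuation, which are a separate matter.

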16.0 Statistical Analysis

Power analysis

The effect sizes observed in the completed Prasad et al. 2012 study were used to estimate the sample size necessary for adequate power to detect differences in cognitive variables for the current study. The earlier study, which enrolled 12 patients in each group, saw changes in cognitive function with effect sizes that ranged from small ($d=0.25$) to quite large ($d=1.21$). An intent-to-treat (ITT) analysis will be adopted, which includes all randomized subjects. We will use two cognitive domains from the MATRICS battery, visual memory and working memory, as the primary outcome variables. Prasad reported effect sizes of Cohen's $d=0.79$ for working memory and $d=0.97$ for visual object learning when comparing valacyclovir to placebo in HSV-1-seropositive subjects. Forty percent of patients with schizophrenia are HSV-1 positive (Prasad et al in press; Dickerson et al 2003). A total of 175 subjects will be enrolled at 5 sites, with the expectation that 70 subjects will be HSV-1-seropositive and 105 subjects will be seronegative. With 70 HSV-1 positive subjects enrolled (35 per treatment group), we would be able to detect a minimum effect size of $d=0.63$ (a conservative estimate based on the Prasad study) for each of the two primary outcome measures at significance level $\alpha=0.05$ using two-sided t tests. The Hochberg modification of the Bonferroni method to control Type 1 error will be used. With this method, the smallest of the p-values for the two outcomes is tested at $p<\alpha/2$; if that test is rejected, the second outcome is tested at $p<\alpha$. We will achieve the same power when testing HSV-1 positive vs. negative subjects who are on valacyclovir using similar methods. We will test the treatment effects on the two primary efficacy measures (visual and working memory) with one-tailed tests at an overall $\alpha=0.1$. Stratified randomization will be used to ensure the balance of HSV-1 status between the valacyclovir group and the placebo group.

Data Analysis

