The primary objective of this study is to determine: 1) whether valacyclovir improves cognitive functioning in schizophrenia subjects who are HSV1 seropositive and early in the course of their illness, and 2) whether the improvement from valacyclovir differs in HSV1 seropositive and negative subjects. We hypothesize that subjects who received valacyclovir will show improvement in memory functioning, as measured by the visual and working memory domains of the MATRICS cognitive battery relative to their counterparts who received placebo, and the improvement exists in HSV-1 seropositive subjects compared to the seronegative subjects. All randomized subjects will be used using ITT analysis. This is the most conservative approach for detecting a treatment effect, because the inclusion of subjects who did not complete the intervention will serve to underestimate rather than overestimate any treatment effect. Sensitivity analyses including a subset analysis using completers only analysis will also be performed to test the robustness of the findings. Statistical tests will be performed based on one-sided test at the 10% level of significance with an adjustment for multiple comparisons for the 2 primary efficacy outcome measures with each primary measure tested at an alpha threshold of $p<0.05$ as noted above. One-tailed tests are planned because the main interest of this study is to

determine if valacyclovir is superior to placebo and thus has produced a sufficient efficacy signal in one or more of the two primary efficacy outcome measures to warrant further assessment in subsequent larger, confirmatory trials.

Baseline analysis will be conducted to summarize patients' characteristics in the two treatment groups for HSV-1 seropositive and seronegative subjects respectively. Demographics and relevant clinical variables, including symptom severity and antipsychotic dose equivalents, will be compared between treatment groups using two-sample t tests (for continuous variables) and chi-square tests (for categorical variables).

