The primary outcome measures are the visual and working memory domains of the MATRICS battery. For each subject, a change score will be calculated for this domain, which quantifies the difference in cognitive performance from pre-treatment baseline to post randomization study visits. Unadjusted p-values from direct comparison of valacyclovir vs. placebo among HSV-1 positives, and HSV-1 positive vs. negative with active treatment will be reported using two-sample one-sided t tests.

The primary outcome measures (visual memory and working memory) and important secondary cognitive (MCCB composite score) and functional (UPSA-B, Q-LES-Q-SF) outcome measures will be assessed at baseline, visit 6 and visit 10. To analyze these measures, we will employ a mixed model for repeated measures ANCOVA, of the general form for each measure: Post-baseline score at visit i = baseline score + treatment + visit + HSV-1 status + interactions among treatment, visit, and HSV-1 status + other baseline covariates, where visit is a categorical measure denoting whether the post baseline score came from visit 6 or 10. Within-subject correlation will be modeled with an unstructured covariance matrix with 3 parameters (variances at visit 6 and 10, covariance between visits 6 and 10). In this model, the treatment effect estimates the average magnitude of the treatment differences at visits 6 and 10, and the treatment x visit interaction the difference in the magnitude of the treatment difference at visit 10 vs visit 6. Additional interactions involving treatment, HSV-1 and week estimate how the magnitude of treatment differences, on average or at visits 6 versus 10, is altered by HSV-1 status. No imputation will be needed to address missing data issue using the linear mixed model approach.

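### The ITT analysis is called conservative, but testing after discontinuation is discretionary and the primary model uses only observed scores, so that property is not secured

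*Combined protocol and SAP*

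**What the plan says.** Section 16.0 (Power analysis) commits to the analysis set: "An intent-to-treat (ITT) analysis will be adopted, which includes all randomized subjects". The Data Analysis part adds "This is the most conservative approach for detecting a treatment effect", on the ground that "the inclusion of subjects who did not complete the intervention will serve to underestimate rather than overestimate any treatment effect".

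Section 10.0 governs what happens when someone stops. It opens its list with "Subjects will be discontinued under the following circumstances"; the list includes non-compliance, laboratory values and excluded medication. It does not say whether the subject leaves the study or only the study medication. After the list it says "If a subject discontinues from the study, discontinuation assessments will be at the discretion of the investigator", and then, separately, "A subject may withdraw from the study medication at any time at his/her own request".

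Attachment 1 schedules the cognitive battery at visits 2, 6 and 10. The column headed Termination is visit 10, day 112. There is no early-termination visit and no rule for assigning an early score to a visit.

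For the primary outcomes, section 16.0 fits a repeated-measures mixed model to post-baseline scores at visits 6 and 10, with baseline as a covariate, and says "No imputation will be needed to address missing data issue using the linear mixed model approach". The one sensitivity analysis it names is this: "Sensitivity analyses including a subset analysis using completers only analysis will also be performed to test the robustness of the findings". Multiple imputation is planned for the CGI only.

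**The concern.** Keeping non-completers in an analysis pulls the estimate toward zero only if they have outcome data from after they stopped, or values are assigned to them. The plan secures neither. A subject with no visit 6 or visit 10 score adds nothing to the estimated treatment effect, although nominally in the ITT set; a subject with only a visit 6 score adds only that.

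A mixed model under missing at random is a defensible choice. The error is to describe its result as conservative for all randomised subjects. Section 16.0 says the trial is to show whether there is enough of an efficacy signal to justify larger confirmatory trials. An effect size wrongly believed to be a lower bound could lead to follow-on trials that are too small, and scores not collected after stopping cannot be recovered.

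**Working it through.** **Inputs from the plan.** 35 HSV-1 positive subjects per arm and d = 0.63 (section 16.0, Power analysis); a one-sided threshold of 0.05 per primary measure (section 16.0, Data Analysis); test-retest reliability of about 0.7 for most tests (section 8.0).

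**Not in the plan.** There is no planning dropout rate, so no stated figure can be reproduced on this point. Section 2.0 says pilot dropout was similar between arms but gives no rate. Its 5.1% covers adverse-event discontinuation only, in genital herpes patients at lower doses. Dropout of 10%, 20% and 30% is therefore assumed.

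**Step 1: benefit lost on stopping.** Let q be the share of the valacyclovir arm that leaves, f the share of leavers who go after visit 6 (benefit kept at visit 6, lost at visit 10), and delta the effect while on drug. Then:

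- effect in all randomised subjects, averaged over visits 6 and 10 = (1 − (1 − f/2)q) × delta
- overstatement by the model = 1/(1 − (1 − f/2)q) − 1

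| q | all leave before visit 6 (f = 0) | all leave after visit 6 (f = 1) |
|---|---|---|
| 10% | 1/0.90 − 1 = 11% | 1/0.95 − 1 = 5% |
| 20% | 1/0.80 − 1 = 25% | 1/0.90 − 1 = 11% |
| 30% | 1/0.70 − 1 = 43% | 1/0.85 − 1 = 18% |

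With delta = 0.63 and q = 20%, the all-randomised effect is 0.63 × 0.80 = 0.504 (f = 0) or 0.63 × 0.90 = 0.567 (f = 1). An even split (f = 0.5) gives 0.63 × 0.85 = 0.54. A simulation of the planned model with 20% random dropout per arm returned about 0.63 in each case. When there is no true effect there is no benefit to lose, so the test keeps its level.

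**Step 2: no true effect, dropout unequal and related to outcome.** Simulation assumptions: baseline, visit 6 and visit 10 scores equally correlated at 0.7; all dropout before visit 6; 30% on valacyclovir against 10% on placebo; a latent tendency to drop out that correlates r = 0.3 or 0.5 with a worse post-baseline score. Bias in SD units:

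| Estimate | r = 0.3 | r = 0.5 |
|---|---|---|
| Single visit, baseline-adjusted | about +0.05 | about +0.08 |
| Visit 6/10 average, baseline-adjusted | +0.03 to +0.04 | about +0.06 |
| Single visit, change score | about +0.03 | about +0.045 |

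Swapping the rates reverses the sign. At 20% against 10% the bias is about half as large. At equal rates it is about zero.

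**Step 3: rejection rate.** With 35 per arm, 20,000 simulated null trials and a one-sided 0.05 test of the baseline-adjusted average:

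- 30% against 10%: about 7% to 8% (r = 0.3) and about 10% (r = 0.5)
- rates swapped: about 3% and 2%
- equal 20% dropout, r = 0.5: about 5%

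**Step 4: does the completers-only analysis help?** In the simulation with a true 0.63, 20% random dropout per arm split evenly around visit 6, and benefit lost on stopping, the visit 10 estimates were 0.63 (mixed model) and 0.63 (completers only), against 0.50 in all randomised subjects. Completers-only analysis discards the same post-stopping experience, so it neither tests the missing-at-random assumption nor bounds the bias.

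**The case against.** There is a reasonable case on the other side.

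- **Study versus medication.** The discretion in section 10.0 attaches to leaving the study; withdrawal from medication is a separate sentence, and Attachment 1 does not make visit 6 and 10 testing conditional on being on drug. Investigators may also still test. This stands in part: the plan can be read that way. But it never says that those discontinued under the list stay in follow-up, and discretionary testing at five sites can be selective.
- **Conservative relative to what?** The next sentence names the completers-only analysis, so the claim may mean conservative compared with completers. Even so it is not guaranteed: in step 4 the two estimates coincide.
- **Evidence on dropout.** The pilot reported similar dropout by arm, and the genital herpes study in section 2.0 reports similar discontinuation across its groups, placebo included. Section 16.0 also compares retention time across arms, and the monitoring boards in section 15.0 review dropout. This stands against the false-positive scenario: 30% against 10% is an assumption with no support in the documents, and a large imbalance would be seen. It does not touch step 1, which needs no imbalance, and seeing dropout does not restore missing scores.
- **Two estimands, not an error.** The effect had subjects stayed may suit a signal-finding trial. That is arguable, but then the plan should say so and not call the result conservative for everyone randomised.
- **Open list.** The sensitivity analyses are introduced as including completers only, so others are possible. None is named that addresses the assumption for the primary outcomes.

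**Conclusion.** The concern holds. As written, the plan does not have the property it claims: neither the data collection nor the model makes the estimate an underestimate of the effect in all randomised subjects. The direction is simply not guaranteed; the trial need not overestimate.

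The consequence is limited. The overstatements in step 1 assume that every leaver loses all benefit; they shrink if benefit persists, and the significance test is not affected. The inflated rejection rates in step 3 require unequal, outcome-related dropout before visit 6. This should be corrected, but it does not invalidate the primary test.

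**What to change.** - **Section 10.0:** separate stopping study medication from leaving the study. State that subjects who stop medication are still asked to attend the scheduled visit 6 and visit 10 testing of the two primary domains unless they withdraw consent. Those domains are already given first in the battery. The medication-stopping rules are not changed.
- **Section 16.0, Data Analysis (model):** include those scores at their scheduled visits in the mixed model.
- **Section 16.0, Data Analysis (ITT text):** delete the statement that the approach is conservative and underestimates the effect. Add one missing-not-at-random sensitivity analysis for the two primary outcomes, for example control-based or delta-adjusted.

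The cost is wording in the protocol and SAP, with no new visits or instruments. The downsides are some effort to keep off-drug subjects attending two tests, and a possibly smaller estimated effect.
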